Pyrethroid phenotypic resistance prevalence and intensity (and PBO effects thereon)

Diagnostic dose bioassays are widely used but typically insensitive measures of insecticide resistance, but can be improved by addition of further assays using higher concentrations of insecticide to segregate more highly resistant females (CDC 2016; WHO 2017). A key component

Figure 9. Health zones and distribution with feasible daily travel for mosquito collection and return to Gemena indicated by the dashed circle. It is planned that bloodfed females will be collected from locations within this zone and their offspring used for phenotypic assays of resistance and LLIN bioefficacy

of the testing procedure is the use of PBO as a pre- or co-exposure pyrethroids to determine any evidence of loss of efficacy of PBO. We propose to test 3 different concentrations (+ no insecticide controls) of deltamethrin with and without PBO, using standard WHO tube test procedures on representative mosquitoes collected from two separate PBO and non-PBO zones (Figure 8). This yields a total of 2 arms x 2 collection locations x 4 concentrations x PBO+/- = 32 treatments, each of which will be represented by 4 replicate tubes of N=25 3-5 day old female *An. gambiae* s.l. The plan is shown below.

- Deltamethrin 1x (diagnostic dose)
- Deltamethrin 5x
- Deltamethrin 10x
- Deltamethrin 1x with PBO pre-exposure (if 1x does not kill 100%)
- Deltamethrin 5x with PBO pre-exposure (if 5x does not kill 100%)
- Deltamethrin 10x with PBO pre-exposure (if 10x does not kill 100%)

The large number of mosquitoes required for testing at each period (6 monthly) suggests that a flexible approach is necessitated a priori until availability of different collection sources can be assessed during initial entomological surveys (above). There are two possibilities: collection of larvae (and rearing to adults), or collection of blood-fed females using more exhaustive prokopak collections and testing of their F1 offspring. Each methodology has logistical pros and cons but results are expected to be broadly comparable, provided the number of larval habitats sampled or egg batches raised is large enough to give a fair representation of the local mosquito population.

In addition, if sufficient females are available, additional insecticides can be tested on a more limited scale, for example the other major LLIN pyrethroids permethrin and perhaps alpha-cypermethrin or perhaps newer LLIN insecticides such as chlorfenapyr, which if samples of BASF Interceptor G2 were available might be best tested directly in assays on Sud Ubangi mosquitoes.

Net efficacy and lifespan

We need to know when nets start to lose integrity, so that a reduction of impact due to loss of coverage can be distinguished from a reduction of impact due to loss of insecticide. A simple durability monitoring protocol will record holes (and proportionate hole index calculated), coupled with bioassays on the nets, as well as chemical tests done to assess the quantity of deltamethrin and PBO present on the nets. Specifically, bioefficacy will be measured via WHO cone tests using locallycollected mosquitoes (see Figure 9 for collection areas) on sections of LLINs (with separate tests for upper and side panels for Permanet 3) removed from the field (and replaced) at time intervals of 6 months. The LLINs to be removed can be selected randomly from the houses identified for entomological collections above at the end of the mosquito sampling period. Sections of the same LLINs will be tested for active ingredient concentration (with separate tests for upper and side panels for Permanet 3) using HPLC analysis at LSTM. Per collection period we plan to remove an LLIN from a random selection of 10 houses from villages around health centres from 3 zones/arm, giving a total of N=30 LLINs per arm per time point. The 30 LLINs per arm will be tested using one bioassay cone per net for PermaNet 2 (standard) and two for PermaNet 3 (top and side) yielding a total required number of female mosquitoes for testing of N=900. Collections for these would be made at the same time as for insecticide susceptibility tests.

Household recruitment

Mosquito collections

Following initial contact between the head of each village to be included, randomly identified households (from a GPS list collected during planning for the LLIN distribution by IMA the distribution coordinators) within villages will be visited by study personnel, accompanied by a village resident. If householders are present, the purpose of the study and nature of collections will be explained to them, and if they are willing to be enrolled the head of the household will be asked to sign a consent form the following day, which will give potential permission (subject to verbal consent at the time of collection) to collect from the house on up to 6 occasions at 6 month intervals. If they do not wish to take part, or the head of the household is absent, a neighbouring house will be approached. Owing to the possibility that verbal consents will not be given, or householders may not be present in the property at the time of the collections (between 6am and 10am) we aim to consent

approximately 30% more households than will be sampled, and will call to inform those not included as soon as possible on the collection morning.

LLIN durability

Householder recruitment for quantification of LLIN integrity and removal sampling of LLINs will proceed in the same way as for mosquito collections, albeit on a much smaller scale and involving only a single visit per house. The houses will be different to those included in the mosquito collections and a separate information sheet and consent form will be used.

Additional work of interest but not currently planned or costed for:

Human behavior and malaria risk (highest priority)

The capacity of LLINs to protect is determined by human and mosquito behavior (timing and location of biting). The former can be assessed using simple questionnaires to determine location and sleeping times, and the latter is best assessed using human landing catches (HLCs) conducted indoors and outdoors, recording biting times of mosquitoes (Figure 4), which is quite expensive. If complementary funding became available it would be extremely informative to include this component in the study

Age distribution of the mosquitoes

Successful interventions targeting adult mosquitoes are expected to shift the age distribution of adult females downwards, which is an important component of their success because it reduces the relative proportion of females that have lived long enough for infecting *Plasmodium* to pass through their incubation period and become infective sporozoites. Unfortunately, mosquito age is difficult to assess, and currently most methods lack accuracy and/or are extremely time-consuming. However, methods based an expanded gene expression panel are currently under evaluation (LSTM, MRC Gambia collaboration), as are other methods for molecular analysis including mid-infra red spectroscopy (developed at University of Glasgow, UK). We will preserve a portion of samples in a way suitable for these kind of analyses (in RNALater preservative for gene expression or dried for MIR spectroscopy).

Molecular surveillance of additional local resistance mechanisms and broader genomic/transcriptomic changes

Samples gathered for DNA analysis (dried specimens) or for gene expression analysis (in RNALater) can also be used for comparative analysis of additional mechanisms of insecticide resistance (i.e. beyond *kdr* and the Cy6P haplotype markers) as they become available from ongoing work at LSTM.

Molecular surveillance of Plasmodium falciparum strain identity and diversity

Mosquito samples testing positive for infection can also be used as a source of *P. falciparum* to investigate genetic diversity (strain variation) using a molecular barcoding approach to type different strains.

Key deliverables

- 1. Epidemiological assessment of the efficacy of conventional and PBO-treated LLINs using ANC prevalence data
- 2. Assessment of the selective impact of different LLIN types on the local mosquito populations targeted using molecular entomological surveillance

- 3. Assessment of the impact of LLIN type on cases of uncomplicated and severe malaria as recorded in DHIS2
- 4. Assessment of the impact of different LLIN types on the local mosquito abundance, sporozoite rates and entomological inoculation rate
- 5. Assessment of the lifespan of different LLIN types from entomological assessment of bioefficacy, chemical analysis of active ingredients, and measurement of the physical integrity of a sub-sample of LLINs
- 6. Assessment of the effect of LLINs on phenotypic variation in resistance over time, including to the synergist PBO

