Sud Ubangi and LLINs: AMF have purchased approximately 1.9 million LLINs for Sud Ubangi province. LLINs are projected to arrive for distribution in November 2019 and will be distributed to the 16 health zones in Sud Ubangi (Figure 1). The 16 health zones (zones de santé) serve approximately 3.3 million people, in a total province area of approximately 52,000 km².

Figure 1. Map of Sud Ubangi health zones and the number of operational health areas per health zone in relation to population size

Population density is generally low, but is notably highest in the province capital Gemena, which has an airport served by twice weekly Congo Airways flights from Kinshasa. With the exception of the airport road in Gemena, paved roads are absent throughout the province, and degradation is likely to affect transport logistics, especially in the wetter months of the year (typically July-September). Health zones are divided into health areas (aires de santé), the numbers of which vary roughly in relation to population density (Figure 1). The boundaries of these health areas are not always precisely mapped, but each health zone's central hospital has a list of operational health areas, each of which is served by a health centre or (smaller) health post, the distances of which from each central hospital are recorded and hand-drawn maps are usually available locally. Socioeconomic status is generally low and housing near-ubiquitously of the traditional mud brick and thatch (photograph below).

Malarial epidemiology: Cases of malaria do not appear to be strongly seasonal in Sud Ubangi, although some slight decreases might occur during the drier months (December-February/March) (Figure 2). Testing rates are extremely high, barring a relatively short RDT stockout period in October-November 2018, and a very high and consistent percentage of suspected cases are confirmed by tests. Over 95% of infections are *Plasmodium falciparum* with few cases attributed to *P. ovale* and *P. malariae*. The number of recorded cases appears to have been increasing from the start of the DHIS2 recording period at the beginning of 2017. Whether this is a true reflection of prevalence, as a result of bednets beginning to lose integrity (Janko et al. 2018) after the 2016 distribution, or a result of improved data gathering is not clear.

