Data on mosquito abundance, infective *Plasmodium infection* rate, entomological inoculation rate (EIR), and human biting rates are all lacking for Sud Ubangi or any comparable province. Preliminary data obtained during our scoping study in late April 2019 via human landing catches gives some insight into biting patterns. The mosquito genera captured were *Culex* sp. (51%), *Mansonia* sp. (19%) and *Anopheles* species (30%), with similar total catches of the latter indoors and outdoors

Figure 4. Human landing catch collections of *Anopheles* performed inside and outside five houses in a village near Karawa, Nord Ubangi (50 km east of Gemena) on 25/04/19

(Figure 4). Outdoor collections were close to houses, and do not provide evidence of an outdoor biting mosquito phenotype. Overall, these limited data suggest most biting occurring between about

9 pm and 5 am, a period during which younger children at least are likely to be sleeping and for much of which all residents may be protected by LLINs. Investigation of human behavior in relation to mosquito biting activity will be interesting to understand risk of exposure and the period during which LLINs are capable of being effective.

Ante-natal clinic data: ANC data are available from DHIS2, and include number of first visits (ANC1) and symptomatic malaria cases and test rates in the women presenting. Prevalence rates are not available because there is no routine testing, only SP preventative distribution as per

Figure 5. Monthly ANC visits for each health zone from DHIS2 data gathered from each health centre within aires de santé in 2017-18. Boxes show 25-75 percentile range, with median line indicated, and whiskers show 5-95% range. Circles are values for centres falling outside of the range and asterisks show statistical outliers. The overall average is shown by the dashed line.

national policy. With the exception of an extreme outlier (top left in figure 7), there is reasonable consistency in the number of ANC1 visits per health centre per month across health zones. Notably, at least 7 health centres have at least 20 ANC1 visitors per month for every zone (and most many more) suggesting these can serve as useful *minimum* values for number of available health centres and ANC1 visitors for prevalence testing.

		Cumulative remainder	Cumulative remainder	Final assignment
Health Zone	Net Need	non-PBO	РВО	Final assignment
Budjala	86,263	847,237	933,500	Non-PBO
Bwamanda	151,440	847,237	782,060	PB0

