Bogosinubia	105,780	741,457	782,060	Non-PBO
Gemena	232,158	741,457	549,902	PB0
Libenge	146,629	594,828	549,902	Non-PBO
Mawuya	97,755	497,073	549,902	Non-PBO
Mbaya	40807	497,073	509,095	PBO
Tandala	177,066	497,073	332,029	PBO
Bulu	90,793	406,280	332,029	Non-PBO
Kungu	137,104	269,176	332,029	Non-PBO
Bangabola	119,323	269176	212,706	PBO
Bominenge	97,143	172,033	212,706	Non-PBO
Bokonzi	136,110	172,033	76,596	PBO
Ndage	85,008	87,025	76,596	Non-PBO
Boto	113,992	-26,967	76,596	87,025 Non-PBO + 26,967 PBO

Randomisation and proposed LLIN-type distribution plan

Zongo	49607	-26,967	26,989	PB0	
-------	-------	---------	--------	-----	--

The proposed assignment uses the same adaptive randomization methodology used in the ongoing Uganda LLIN-UP trial. The process involves: (1) A value of 0 or 1 is randomly assigned to each cluster (zone), with assignment of the first cluster from a coin toss. (2) Cumulative probability ranges are generated for each net type based on the targeted number of each individual type of net / targeted number of total nets. (3) The second cluster is assigned to intervention-arm based on which cumulative probability range the corresponding random number fell into. (4) Steps 2 and 3 are repeated after removing the number of targeted nets assigned to the cluster for the corresponding type of net and the total number of nets. (5) The process is repeated until all clusters are allocated to an intervention.

The geography of the LLIN distribution plan is shown in Figure 6. Although during our scoping visit we were unable to obtain accurate information on travel times from Gemena to outer locations, our experience during recent visits suggests that travel times are unlikely to exceed an average rate of 30km/ hour and may be slower after heavy rains.

IMA world health will be organizing the logistics of the LLIN distribution including a per house hang-up programme involving GPS location of every house.

Boto mixed LLIN distribution zone

Figure 6. Map of Sud Ubangi health zones showing those randomised to receive PBO LLINs (blue); standard LLINs (white) or a mixed zone (blue/white)

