There needs to be one mixed assignment zone (Boto), which will primarily be a non-PBO distribution (see Table). For reasons of study power (below) it is crucial to organise the distribution such that the net types cluster around health centres used for assessment, to ensure that the zone can be retained as a cluster for at least one and hopefully both LLIN types in the study. The number of available PBO LLINs represents just under 25% of the total net need for Boto. As a result of logistical considerations and also to reduce the potential for mosquito dispersal between clusters with different types of LLIN a distribution plan to a cluster of western aires de sante is proposed for Boto (Figure 7).

Figure 7. Map of Boto health zone showing the western areas of Bomele, Bombili, Bobandu and Bokozo proposed to receive PBO LLINs (blue); all other areas will received standard LLINs. ?-1,2 show uncertain boundary locations between zones

If projected LLIN needs for each of the four areas are accurate, this would leave 2,000 surplus PBO LLINs, which could be distributed as close as possible, i.e. preferably along borders of these aires de sante to expand the size of the PBO-LLIN cluster.

More generally the mixed distribution in Boto could provide an important template for future distributions to provinces where division into fewer zones would preclude a statistically-useful comparative study if LLINs of contrasting types were distributed solely at the zonal level. Whilst statistically a distribution fully randomized at the level of aires de sante would be powerful, this is logistically challenging, may lack visible mapped impact on a malaria data map. Grouping of aires de sante - in the way proposed for Boto - could provide a viable intermediate distribution plan to meet statistical requirements, and, in addition to relative logistical ease also has the advantage of reducing the impact of human, net and mosquito movements among net-type clusters.

Proposal hypotheses and endpoints

Epidemiological

Primary

Hypothesis: PBO LLIN distribution will result in a lower malaria prevalence than standard (non-PBO) LLINs as indicated by reduced prevalence in ANC1 visitors.

Endpoint: monthly malaria prevalence in ANC1 visitors measured using RDTs, with main assessment points at 6 monthly intervals and intermediate assessments quarterly.

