Sample size calculation and power: From preliminary analyses it was evident that a minimum 8 vs 8 cluster/ arm trial would be required to adequately power the study to detect plausible effect sizes using a relatively simple cluster arm comparison for a single month's data (temporal variation is unknown so it is difficult to include multiple months in *a priori* power analysis). We used fixed assumptions for the number of available health centres/ zone of N=7 and number of ANC1 visitors

per month of N=20, giving a cluster size of N=140. Note that varying the cluster size has only a moderate impact on power, provided health centres are chosen randomly from those available. Parameter values for the inter-cluster coefficient of variation (*k*, which has a large impact on power) were estimated from DHIS2 2018 data from the rate of positive malaria tests per month per capita (i.e. data divided by population size of zone) as a proxy. Following equation 9 in Hayes & Bennett (1999) we calculated k=0.18 from these data. However, noting this is lower than estimated from the only comparable published study from Tanzania (k values of 0.20-0.28 depending on survey round; West et al. 2014) we also examined a 'high COV' value of k=0.3.

Similarly we lacked information on the baseline prevalence of malaria for Sud Ubangi, with the last survey in 2013-14 detecting a rate of 24% in children under 5 (MPSMRM 2013-14), which using a conversion factor of 1.44 between child and pregnant women's prevalences (van Eijk et al. 2015) we used to estimate an ANC prevalence value of 17%, which is also very close to the average figure for the DRC ANCs presented in Hellewell et al. (2018). However, figures in Hellewell vary greatly and thus because of the considerable uncertainty in this point estimate, we examined a range of possible prevalence rates (applicable to the standard-LLIN reference arm).

We identified the minimum detectable reduction in prevalence using equation 4 from Hayes & Bennett (1999) with the following study design parameters:

Arms=2; Clusters (zones)/arm = 8; subjects/ cluster = 140; k = 0.11 or 0.30; α =0.05; power =80%; prevalence in reference standard-LLIN arm (π 0) varied between 5 and 50%

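### The net-weighted draw controls neither zones per arm nor stock fit, so the proposed allocation has seven whole PBO zones, eight whole standard zones and a split Boto instead of the stated 8 vs 8 minimum

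*Protocol*

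**What the plan says.** The section on randomisation and the proposed LLIN-type distribution plan describes a five-step sequential draw:

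- Step 1: "A value of 0 or 1 is randomly assigned to each cluster (zone), with assignment of the first cluster from a coin toss".
- Step 2 builds probability ranges from each net type's share of the nets.
- Step 3: "The second cluster is assigned to intervention-arm based on which cumulative probability range the corresponding random number fell into".
- Steps 4 and 5 subtract the assigned nets and repeat until every zone is placed.

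No step fixes the number of zones per arm or checks that the next zone's need can be met from one stock.

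The table in that section keeps running remainders and ends with Boto receiving both net types. The text below it says "There needs to be one mixed assignment zone (Boto), which will primarily be a non-PBO distribution (see Table". Four western aires de santé are to receive PBO nets, chosen for logistics and to limit mosquito movement between net types. On projected needs "this would leave 2,000 surplus PBO LLINs", to be placed along the borders of those aires.

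The epidemiological sample size section says "a minimum 8 vs 8 cluster/ arm trial would be required to adequately power the study". It treats Boto as a possible additional standard cluster and keeps 8 vs 8. The section on inclusion of health centres requires seven aires per zone, drawn at random from those with more than 20 ANC1 visitors a month.

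**The concern.** The power statement and the design summary both rest on eight zones per arm, but the allocation supplies only seven whole PBO zones. The eighth can only be the PBO part of Boto, which fails the design's own rules in two ways. It has four aires where seven are needed, and those aires were selected by hand where the plan calls for random selection. The sample size section makes its reassurance about cluster size conditional on random choice of health centres.

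The same part-zone appears elsewhere. The entomological plan samples three whole zones per arm plus both parts of Boto, so one of four clusters in each arm is a non-randomised part of a zone. The DHIS2 case rates use population estimates per health zone, which do not divide by arm inside a split zone.

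**Working it through.** **Inputs (protocol table and text).** The first row, "Budjala 86,263 847,237 933,500 Non-PBO", gives the PBO stock as 933,500 and the standard stock as 847,237 + 86,263 = 933,500. Together these are 1,867,000, in line with the approximately 1.9 million nets bought. The 16 net needs sum to 1,866,978, leaving a slack of 22 nets over both types.

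**Reproducing the table.** Subtracting each zone's need from its assigned stock reproduces every row.

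- At Boto's turn the need is 113,992, with 87,025 standard and 76,596 PBO nets left, so neither stock covers it.
- Zongo (49,607) then takes PBO nets, leaving 76,596 − 49,607 = 26,989.
- Boto's shortfall is 113,992 − 87,025 = 26,967, a PBO share of 26,967 / 113,992 = 23.7%. This agrees with the protocol's statement of just under a quarter.
- Whole PBO zones: Bwamanda, Gemena, Mbaya, Tandala, Bangabola, Bokonzi, Zongo (7; need 906,511).
- Whole standard zones: Budjala, Bogosinubia, Libenge, Mawuya, Bulu, Kungu, Bominenge, Ndage (8; need 846,475).

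**What the stock permits.** I enumerated all C(16,8) = 12,870 labelled 8 vs 8 allocations and counted those in which neither arm's need exceeds 933,500 by more than a tolerance:

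| Tolerance (nets) | Labelled 8 vs 8 allocations |
|---|---|
| 0 | 2 |
| 500 | 48 |
| 1,000 | 94 |
| 2,000 | 196 |
| 5,000 | 484 |

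The two exact fits are one partition and its mirror:

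- Budjala, Bwamanda, Bogosinubia, Libenge, Bulu, Bangabola, Bominenge, Bokonzi (933,481)
- Gemena, Mawuya, Mbaya, Tandala, Kungu, Ndage, Boto, Zongo (933,497)

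At a tolerance of 2,000 (2,000 / 933,500 = 0.2% of an arm's stock), each zone is in either arm in half of the 196 allocations. The proportion in which a given pair of zones shares an arm runs from 0.24 to 0.69 over pairs. Unconstrained 8 vs 8 randomisation would give 7/15 = 0.47.

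**What the stated draw delivers.** I simulated the draw in table order, with the probability of PBO equal to PBO nets left divided by all nets left.

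- Eight zones per arm by label: about 45% of draws.
- Shortage above 2,000 nets: about 94%.
- Median shortage: about 22,500 nets.
- Both 8 vs 8 and a shortage of at most 2,000: about 2%.
- Any exact whole-zone fit: about 0.06%.

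**Effect on power.** For c₀ standard and c₁ PBO clusters I used the unmatched formula with coefficient of variation k, extended to unequal arms:

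(π₀ − π₁)² = f [ v₀/(c₀ − 1) + v₁/(c₁ − 1) ], where v = π(1 − π)/140 + k²π² and f = (1.96 + 0.84)² ≈ 7.85.

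At π₀ = 0.17 and k = 0.18, v₀ = 0.001944.

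- 8 vs 8: π₁ = 0.1115, v₁ = 0.001110; both sides equal 0.003425. Detectable reduction 34.4%.
- 8 vs 7: π₁ = 0.1099, v₁ = 0.001091; both sides equal 0.003607. Detectable reduction 35.3%.

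The protocol also lists k = 0.11 and 0.30. The corresponding pairs are 29.7% and 30.6%, and 44.2% and 45.1%.

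**The case against.** A reader might infer that the protocol's sentence is simply false and that a mixed zone is fully avoidable. The documents do not support that. The sentence points to the table and, for this draw and stock, it is true. With 22 spare nets, restricting the draw to exact fits would leave one coin toss between two fixed groups of zones, which is not a usable randomisation. Any workable tolerance leaves a small quantity of the other net type somewhere.

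Other points against the concern also stand:

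- The 2,000-net tolerance is a reviewer's assumption. The 2,000 surplus in the Boto plan is spare PBO stock and not an accepted overrun, so it does not justify the tolerance.
- The power loss is under one percentage point. If Boto's standard part serves as a ninth standard cluster, the same formula gives 34.1% for 9 vs 7, which is no loss. The split does not make the trial underpowered.
- Mean need is 906,511 / 7 = 129,502 in whole PBO zones against 846,475 / 8 = 105,809 in whole standard zones (22% larger). Most of this is one zone, as the row "Gemena 232,158 741,457 549,902 PB0" shows. Without it the PBO mean is (906,511 − 232,158) / 6 = 112,392, about 6% larger. The primary comparison samples a fixed number of centres and women per zone, so this is no evidence of bias.
- A value of 0 or 1 in step 1 is loose wording. Step 3 makes a number between 0 and 1 the evident meaning.
- The protocol discloses the split and values it as a template for provinces with fewer zones.

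None of this supplies an eighth randomised PBO zone, or explains why the draw left the zone count free when eight per arm was called the minimum.

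**Conclusion.** The point holds as a defect of the allocation procedure. Some mismatch with the stock has to be accepted, but one of 26,967 nets does not: within an assumed 2,000 nets there are 196 allocations with eight whole zones per arm. What is at stake is a complete, randomised PBO arm in place of seven whole zones plus four hand-selected aires. Statistical power is a minor part of it.

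The enumeration rests only on the table. The simulated percentages assume table order and probabilities equal to the remaining net shares. The choice of tolerance is open. The change is worth making while the assignment is still described as proposed.

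**What to change.** **If nets are not yet committed.** Replace steps 1 to 5 with constrained randomisation:

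1. Fix a tolerance in advance, for example 2,000 nets.
2. List every 8 vs 8 allocation whose need exceeds either stock by no more than that.
3. Select one by a recorded uniform draw before distribution.
4. Place the small remainder of the other net type in aires without a study health centre. This assumes the affected zone has an aire beyond its seven study aires, to be checked against Figure 1. The four Boto aires average about (26,989 − 2,000) / 4 ≈ 6,200 nets, so a remainder of 2,000 is less than one such aire.
5. Reword the Boto sentence to say that the split followed from the earlier draw.

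**Cost.** No extra nets, women or clinics are needed. The existing draw is discarded, and the record must show that this was done before distribution and without outcome data. The zone plan must be communicated again to the distribution partner ahead of the projected November 2019 arrival. The mixed-zone template is lost, and the two Boto entomology clusters must be replaced by whole zones.

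**If the allocation is committed.** State it as 7 whole PBO zones, 8 whole standard zones and a split Boto. Give the 8 vs 7 detectable reduction beside the 8 vs 8 figure, and correct step 1 to a uniform random number between 0 and 1.
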